Zoledronic Acid to Prevent High-Turnover Bone Loss after Bariatric Surgery

ClinicalTrials.gov ID: NCT03424239

Document Version: January 8, 2019

Zoledronic Acid to Prevent High-Turnover Bone Loss after Bariatric Surgery

I. Background and significance

Bariatric surgery is a highly effective and sustainable method for weight loss [1]. Roux-en-Y Gastric bypass (RYGB) and sleeve gastrectomy (SG) are the most common bariatric procedures performed worldwide, encompassing >85% of all bariatric procedures performed worldwide [2]. Sleeve gastrectomy was introduced within the past decade and has seen an explosion in popularity, now comprising 61% of all bariatric procedures performed at academic medical centers [3]. Although both surgeries lead to dramatic benefits in obesity and obesity-related comorbidities, they are associated with large magnitude bone loss. We have previously documented bone mineral density (BMD) declines on the order of 10% within the first 2 years after RYGB [4, 5] and 5% within the first year after SG [6]. Another study has shown similar rates of bone loss between RYGB and SG procedures in the first 2 years after surgery [7]. Postmenopausal women appear to be at particular risk for a higher rate of bone loss after RYGB than younger women [8, 9]. Furthermore, we have documented parallel deterioration in peripheral bone microarchitecture, with increases in cortical porosity and endocortical resorption, and decreases in trabecular number and density [5, 9]. By 2 years after RYGB, the declines in BMD and microarchitecture translated into a 9-10% drop in estimated bone strength at the radius and tibia, as assessed by micro-finite element analysis. SG has increased in popularity only in recent years and there have not been many studies of changes in skeletal outcomes to date.

We have recently demonstrated that RYGB confers a 43% increased risk of nonvertebral fractures [10]. The higher rate of RYGB-associated fractures was specifically observed for hip fractures and wrist fractures relative to adjustable gastric banding (AGB), a bariatric procedure that is thought to have a relatively neutral effect on bone [11-13]. Another study confirmed that RYGB patients have a 3-5 fold higher incidence of hip, spine, and humerus fractures compared to community fracture rates [14]. Currently there are insufficient data to determine whether SG leads to increased fracture risk [15].

We have performed several studies demonstrating the timing and pattern of rise in bone turnover markers after RYGB. Most notably, C-telopeptide (CTX), a marker of bone resorption, increases as early as postoperative day 10 and peaks at 6 months after surgery, at a range that is 220-245% above baseline values [5, 12, 16]. This marked elevation in bone resorption far exceeds the increases in bone resorption that occur in the settings of non-surgical weight loss, menopausal transition, or immobilization due to 90-day bedrest [17-19]. Longitudinal studies have also noted persistently increased bone resorption in the initial years after RYGB [13, 20, 21], with one recent study reporting CTX elevations of 140% up to 5 years after RYGB [22]. Several studies have also shown significant increases in CTX up to 5 years after SG, though possibly to a lesser extent than after RYGB [6, 7, 23].

Currently there are no effective methods to prevent bone loss in bariatric surgery patients, with studies-to-date focused on non-pharmacologic treatments. The proposed pilot study would be the first to test a pharmacologic agent for the prevention of RYGB- and SG-induced high-turnover bone loss. Intravenous zoledronic acid is ideally suited to prevent the clinically relevant high-turnover bone loss associated with these surgeries. FDA-approved zoledronic acid is a potent

antiresorptive that significantly reduces spine, hip, and nonvertebral fracture risk in osteoporosis [24], and leads to normalization of bone resorption in high-turnover bone disorders, such as Paget's disease, primary hyperparathyroidism, and induced hypogonadism [25-29]. A single dose of zoledronic acid can achieve persistent suppression of bone turnover markers and improvements in bone density for 5 years [30], as well as remissions of Paget's disease for over 5 years [31]. There are currently no studies of the efficacy and safety of zoledronic acid to prevent bariatric surgery- induced bone loss. This pilot trial is powered to answer the important pathophysiologic question of whether a potent anti-resorptive agent can block the powerful increases in bone resorption that are otherwise observed after RYGB and SG.

II. Specific Aims

Our overall aim is to inhibit high bone turnover, prevent bone loss, and ultimately reduce fracture risk in at-risk adults undergoing RYGB or SG. We hypothesize that zoledronic acid can be used safely for this purpose.

Aim 1

Our aim is to evaluate the safety and efficacy of preoperative zoledronic acid treatment on bone turnover in postmenopausal women and older men undergoing RYGB or SG. We will examine 6-month postoperative changes in serum CTX and P1NP, markers of bone turnover, after a preoperative infusion of zoledronic acid in an open-label fashion. We will also employ and refine a perioperative protocol of calcium and vitamin D supplementation, with serial monitoring of serum calcium levels.

Hypothesis: Zoledronic acid safely and effectively inhibits the increases in CTX and P1NP after RYGB and SG.

Aim 2

Our aim is to assess early changes in bone density, and estimated bone strength after preoperative zoledronic acid in postmenopausal women and older men undergoing RYGB or SG. We will utilize dual-energy x-ray absorptiometry (DXA) and quantitative computed tomography (QCT) to preliminarily assess skeletal changes 6 months after RYGB and SG.

Hypothesis: Zoledronic acid attenuates early RYGB- and SG-induced bone loss

III. Subject Selection

This open-label, single arm pilot study is designed as a proof-of-concept study to demonstrate feasibility, determine efficacy of surrogate endpoints (e.g. suppression of bone turnover markers), and to obtain preliminary data about early (6 month) bone density-outcomes.

Inclusion criteria:

1. Women or men planning to receive RYGB or SG surgery
2. Women must be aged ≥ 25 years AND postmenopausal by either of the following criteria
> 36 months since last spontaneous menses; or
> 36 months since hysterectomy, plus serum FSH > 40 units/liter
3. Men must be aged ≥ 50 years

Exclusion criteria:

1. Prior bariatric surgery
2. Weight \geq 400 lbs (due to limitations of bone imaging equipment)
3. Liver disease (AST or ALT $>$ 2 x upper normal limit)
4. Renal disease (serum creatinine $>$ 2.0 mg/dL or eGFR $<$ 35 ml/min)
5. Hypercalcemia (Ca $>$ 10.5 mg/dL) or hypocalcemia (Ca $<$ 8.5 mg/dL)
6. Hypomagnesemia (Mg $<$ 1.7 mg/dL)
7. Serum 25-OH vitamin D $<$ 20 ng/mL

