Participants will receive personalized nutritional (calcium/vitamin D) counseling throughout the study to ensure compliance with guidelines for the postoperative management of bariatric surgery patients [34]. A nutritionist will ensure pre-operative intake of at least 1500 mg/day of calcium through combination of diet and calcium supplements and at least 3000 IU/day of vitamin D. Postoperatively, study subjects will be instructed to take supplemental calcium citrate 1000 mg/day in divided doses as well as vitamin D 3000 IU/day. Subjects will be advised of bariatric formulations of calcium citrate and vitamin D that are chewable, liquid, or quick-dissolve. Furthermore, most RYGB and SG patients at our institution are prescribed a standardized postoperative diet plan that includes ~1200mg of dietary calcium for the initial 2 postoperative weeks. Throughout the remainder of the study, personalized nutritional counseling will ensure post-operative intake (through diet and supplements) of at least 1500 mg/day of calcium and 3000IU/day of vitamin D, in accordance with guidelines for the postoperative management of bariatric surgery patients [34]. Calcium and vitamin D supplements will be provided for all subjects who do not meet these optimal intake levels.

Additional study visits will occur at post-operative weeks 2, 12, and 24 and will include assessments for safety and skeletal outcomes. A skeletal evaluation (DXA, QCT) will again be

performed at week 24. Serum calcium, creatinine, and 25-hydroxyvitamin D will be monitored in real-time throughout the study and if hypocalcemia occurs, we will follow a strict protocol to escalate calcium/D supplements (see Monitoring and Quality Assurance below). An independent Data Safety Monitoring Board will review study progress and any adverse events. This study has been granted IND-exempt status by the FDA. This study is registered on clinicaltrials.gov under NCT03424239.

The following data will be collected:

1. DXA measurements of the lumbar spine, total hip, femoral neck, and total body at baseline and 6-month visit
2. QCT measurements of the lumbar spine at baseline and 6-month visit
3. Anthropomorphic measurements of height and weight at each visit
4. Fasting blood samples for measurements of calcium, albumin, 25-hydroxyvitamin D, and PTH at each visit
5. Batched serum samples will be used to assess levels of bone markers CTX and P1NP at each visit
6. Questionnaires
 - a. Medical history

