 - b. Calcium and vitamin D intake
 - c. Physical activity

Technical Methods

DXA

Dual-energy x-ray absorptiometry (DXA) scans of the lumbar spine, total hip, femoral neck, and total body will be obtained at baseline and 6-month visits (QDR Discovery, Hologic, Inc, Bedford, MA). These scans will be used to assess areal bone mineral density (aBMD). The short-term precision for this technique is 1-2% at the MGH Bone Density Center. The effective absorbed radiation dose for each set of DXA scans is 0.01 mSv.

QCT

Quantitative computed tomography (QCT) scans of the lumbar spine (L1-L2) will be obtained at baseline and 6-month visits (GE LightSpeed Pro CT scanner, GE Healthcare, Waukesha, WI). These scans will be used to assess volumetric bone mineral density (vBMD). Scans are performed with helical acquisition, 1.25mm slice thickness, QCTPro calibration phantom, and the following settings: L1-L2 (120 kVp, 100 mA). 3D reconstructive analysis for volumetric bone density for integral, trabecular and cortical compartments will be performed on QCTPro software (Mindways Software, Inc., Austin, TX). The short-term precision for this technique is 1-2% for vertebral BMD measurements.[35-37] The effective absorbed radiation dose for each set of scans is 1.9 mSv.

Anthropomorphic Measures

Height and weight measurements will be obtained at each visit without shoes using standard protocols.

Questionnaires

A bionutritionist will assess calcium and vitamin D intake using a validated food frequency questionnaire[38] and will provide personalized nutritional counseling. Physical activity will be assessed via the International Physical Activity Questionnaire (IPAQ) long format.[39] A self-administered questionnaire will assess medical history, including fracture history and medication use.

Bone Turnover Markers

Fasting morning blood will be collected at each visit. Serum levels of type 1 cross-linked C-telopeptide (CTX) will be measured by ELISA (Nordic Bioscience, Denmark), with intra- and interassay CV of 1.8% and 2.5%. Serum levels of procollagen type 1 N-terminal propeptide (P1NP) will be measured by RIA (Orion Diagnostica, Finland), with intra- and interassay CV of 6.5% and 6.0%. We will also measure serum 25- hydroxyvitamin D (LC/MS) and PTH (Nichols Institute Diagnostics, San Clemente, CA).

Safety Measures

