Serum calcium and albumin will be measured at each visit. Study subjects will also be assessed for hypocalcemic signs and symptoms. Hypocalcemia, if detected, will be graded according to common terminology for adverse event criteria (CTCAE v.4),[40] with particular attention to symptomatic hypocalcemia and/or grade 2-4 hypocalcemia (<8.0 mg/dL). Hypocalcemia will be addressed with application of an algorithm (see “Data Safety and Monitoring” section below).

VI. Biostatistical Analysis

All analyses will assess the distribution variables, and where appropriate, will employ transformation to combat skew or other irregularities. In addition to assessing study feasibility, the primary outcome of this pilot study is to obtain preliminary data regarding percent change in CTX at 6 months after RYGB and SG. Longitudinal linear mixed models will be applied to compare changes from baseline in CTX and P1NP over the 6-month period. The model will include random individual subject intercepts and fixed time (0, 2, 12, and 24 weeks) effects. Exploratory outcomes include changes in bone density over the 6-month period, which will be assessed by within group t-tests. As a safety measure, this pilot study will also document rates of postoperative hypocalcemia after bariatric surgery. All analyses will be performed using SAS 9.2 software (SAS Institute Inc., Cary, NC).

The primary purpose of this pilot is to obtain preliminary data to inform the design of a larger, statistically powered randomized controlled trial. As such, this pilot study is not powered to detect significant changes in bone turnover markers or bone density.

VII. Risks and Discomforts

Zoledronic Acid

The most common side effects associated with zoledronic acid include flu-like symptoms (e.g., fever, chills, muscle/joint aches) occurring after the infusion. The majority of these symptoms

occur within the first 3 days following drug administration and usually resolve within 3 days of onset but resolution can take up to 7-14 days. Taking acetaminophen or ibuprofen after the infusion can mitigate these symptoms. Other common side effects include nausea, tiredness, dizziness, headache, or pain/redness/swelling at the injection site.

Hypocalcemia

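### Does Aim 2's mention of estimated bone strength, with no strength variable or analysis defined later, require a change to the plan?

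*Combined protocol and SAP*

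**What the plan says.** Aim 2 in Section II names two things to be assessed: "Our aim is to assess early changes in bone density, and estimated bone strength after preoperative zoledronic acid". It then names the tools: "We will utilize dual-energy x-ray absorptiometry (DXA) and quantitative computed tomography (QCT) to preliminarily assess skeletal changes 6 months after RYGB and SG". The hypothesis under Aim 2 speaks of bone loss and does not mention strength.

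The design statement in Section III gives the purpose of the imaging as "to obtain preliminary data about early (6 month) bone density-outcomes".

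The data list in Section V gives modality and site without naming an output, for example "QCT measurements of the lumbar spine at baseline and 6-month visit". The Technical Methods then say what the scans are for. DXA is used for areal density at the lumbar spine, total hip, femoral neck and total body. QCT of L1-L2 is used for volumetric density, and "3D reconstructive analysis for volumetric bone density for integral, trabecular and cortical compartments will be performed on QCTPro software".

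Section VI says: "Exploratory outcomes include changes in bone density over the 6-month period, which will be assessed by within group t-tests". It also states the purpose of the study: "The primary purpose of this pilot is to obtain preliminary data to inform the design of a larger, statistically powered randomized controlled trial". It adds that the pilot is not powered for changes in turnover markers or bone density.

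**The concern.** An aim is a commitment, and a reader expects each outcome in it to lead to a measured variable and an analysis. Strength does not. No site, model, software, unit or test for a strength estimate appears in Sections V or VI. On a strict reading, half of Aim 2 would go unreported. The pilot would then give no estimate of how variable strength changes are, although it exists to supply preliminary data for a larger trial. If an index were added later, nothing in the text would require it to be chosen before the density results were known. In an open-label, single-arm study that leaves room for a selective choice.

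**Working it through.** The question is one of tracing text, so the check sets the sections side by side.

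| Place | Density | Strength |
|---|---|---|
| Section II, Aim 2 statement | named | named |
| Section II, Aim 2 hypothesis | bone loss | absent |
| Section III, design statement | named | absent |
| Section V, data list | modality and site only | modality and site only |
| Section V, DXA and QCT methods | areal and volumetric density | absent |
| Section VI | change by within-group t-test | absent |

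**Count of imaging variables.** DXA gives 4 sites. QCT gives 3 compartments (integral, trabecular, cortical). 4 + 3 = 7 density variables, against 0 strength variables.

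**Could the method be inferred from elsewhere?** The only other mention of estimated strength is in Section I, which reports earlier micro-finite element results at the radius and tibia. The imaging here is DXA of spine, hip and total body and QCT of the spine, so that method cannot simply be carried over.

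**Is there an unlisted scan?** The methods give 0.01 mSv per DXA set and 1.9 mSv per QCT set, each done twice: 2 × (0.01 + 1.9) = 3.82 mSv. This matches the total of about 3.82 mSv under Imaging studies in Section VII. The listed scans account for the whole dose.

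**Does anything depend on a strength variable?** Taking the analyses in Section VI one at a time:
- The primary outcome is percent change in CTX at 6 months. CTX and P1NP are analysed by mixed models that use serum values only.
- Bone density change uses paired DXA and QCT density values.
- Hypocalcemia is a rate based on serum calcium.

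None takes strength as an input, so leaving it undefined alters none of them.

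**Would precision figures size the gap?** No. With 10 completers the 95% confidence half-width for a mean within-subject change is t(0.975, 9)/√10 × SD = 2.262/3.162 × SD = 0.715 SD. That factor holds for any continuous outcome at this sample size. The documents give no SD for strength change, so no percentage-point figure can be supported.

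**The case for a change.** The strongest argument for acting is that the repair is almost free. Deleting the phrase costs only wording. Naming one index for the L1-L2 scans would involve at most 10 × 2 = 20 scans that are already planned, and would remove any freedom to pick an index afterwards. The gap also cannot be closed by looking at the background section.

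Part of this stands: the aim and the later sections do not match, and a reader cannot tell which strength measure, if any, was meant. The rest is weaker.

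- That strength will go unreported is inferred from silence. The data list does not restrict the scans to density, and Section VI's wording for exploratory outcomes is not exhaustive.
- The lost variability estimate matters only if the larger trial would use a strength endpoint, and no section says so. The preliminary data the plan asks for concern feasibility, turnover markers, density and hypocalcemia.
- The documents do not establish that these scans and this software can yield a strength estimate, so defining one is a new choice rather than a correction.
- The risk of a selective choice attaches to an index nobody has proposed, for a descriptive outcome in 10 people.

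**Conclusion.** The inconsistency is genuine but editorial: one phrase in Aim 2, with no defined variable behind it. Its effect on the results the plan specifies is nil, because the CTX, P1NP, density and hypocalcemia analyses can all be carried out and interpreted exactly as written. Deletion would change no output. Specification would add an optional exploratory outcome of unestablished feasibility. If the investigators do report a strength estimate, it would be read as descriptive and unplanned in its details, which is how any exploratory imaging result from a single-arm pilot of this size would be read in any case. No change to the plan follows.

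This rests on two readings of the text: that imaging outcomes are exploratory, as Section VI states, and that the figure not shown in Section IV, which sits among the enrollment text, does not define a strength outcome.

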8. HCT $<$ 32%
9. History of malignancy (except basal cell carcinoma) in the past 5 years
10. History of radiation therapy
11. Significant cardiopulmonary disease (unstable coronary disease or stage D ACC/AHA heart failure)
12. Major psychiatric disease
13. Excessive alcohol or substance abuse
14. Paget's disease, primary hyperparathyroidism, or any other known congenital or acquired bone disease other than osteoporosis
15. Current hyperthyroidism or use of levothyroxine and TSH $<$ 0.1 uIU/mL
16. Current use of loop diuretics
17. Current use or use in the past 12 months of oral bisphosphonates or denosumab
18. Current use or use within the past 3 months of estrogens, SERMs, or calcitonin
19. Any current or previous use of teriparatide, strontium, or any parenteral bisphosphonate
20. Use of oral or parenteral glucocorticoids for more than 14 days within the past 6 months
21. Known sensitivity to bisphosphonates
22. Extensive dental work involving extraction or dental implant within the past 2 months or planned in the upcoming 6 months
23. Aspirin sensitivity with bronchoconstriction

Recruitment:

Study subjects will be recruited from the MGH Weight Center, and if necessary the Brigham and Women's Hospital Program for Weight Management (PWM). Briefly, we will advertise the study using IRB approved materials within Massachusetts General Hospital (MGH) and the MGH Weight Center. Recruitment flyers will be posted in approved locations throughout the MGH (including the MGH Weight Center) and email announcements will be sent through the Partners Clinical Research Program Network. Potential subjects may be identified by their treating physician at the weight center and through the Weight Center surgical scheduling calendar. These subjects will be sent a letter to introduce the study that is co-signed by their treating physician and the study PI. A member of the study staff who is not the treating physician will also explain the study to potential bariatric surgical subjects at a pre-operative visit. With permission from the treating physician at the Weight Center, we may access potential subjects' medical records to confirm contact information and to identify upcoming visits at the Weight Center. Potential subjects will be given a copy of the full consent form to review. They will also be asked permission to be contacted by study staff either during a clinical visit or by phone to further discuss the study.

IV. Subject Enrollment

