We will enroll 10 participants who are planning RYGB or SG surgery. We will enroll men age ≥ 50 and postmenopausal women.

[figure not shown]
To ensure compliance with HIPAA regulations, subjects that will be pre-screened by telephone are informed of the nature and sensitivity of all questions at the beginning of the conversation. They will be asked whether this is an appropriate time for them to answer these questions and told how long the phone call is expected to take.

Subjects will be asked questions about their medical history to determine their eligibility for the study. If they are found to be eligible based on the screening questionnaire, written informed consent for the screening procedures will be obtained by a licensed physician or nurse practitioner. In situations where a nurse practitioner is obtaining consent, subjects will be offered the option for further discussion with a physician investigator if they have any remaining questions. This offer will be documented in the research record, and any consent problems will be reported to the PHRC in real-time. The screening procedure involves a blood draw to assess whether subjects meet all remaining eligibility criteria. If labs and medical history show that all criteria are met, the individual will be invited to enroll in the full study.

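### Inclusion 2 accepts amenorrhea alone as proof of menopause in women with a uterus from age 25, so a younger woman with progestin-related or anovulatory amenorrhea qualifies without an FSH check

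*Combined protocol and SAP*

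**What the plan says.** Section III, Inclusion criteria, item 2 opens: "Women must be aged ≥ 25 years AND postmenopausal by either of the following criteria". Two alternatives follow. The first is "> 36 months since last spontaneous menses; or" and the second is "> 36 months since hysterectomy, plus serum FSH > 40 units/liter". FSH is mentioned nowhere else in the protocol.

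The hormone-related exclusion, item 18 in the same section, covers "Current use or use within the past 3 months of estrogens, SERMs, or calcitonin". Section IV describes the laboratory screen: "The screening procedure involves a blood draw to assess whether subjects meet all remaining eligibility criteria".

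The intended population is stated consistently. Both aims in section II name postmenopausal women and older men, and section IV says: "We will enroll men age ≥ 50 and postmenopausal women". Section IV also fixes the size: "We will enroll 10 participants who are planning RYGB or SG surgery". Section I explains why menopausal status matters to the skeleton: "Postmenopausal women appear to be at particular risk for a higher rate of bone loss after RYGB than younger women".

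**The concern.** The word postmenopausal in inclusion 2 is defined by its two branches, so using it in the opening line adds no further test. For a woman with a uterus the whole definition is an interval since the last spontaneous bleed. An interval of more than 36 months can also arise from a progestin-only method or from chronic anovulation, and the age floor of 25 lets in women for whom those explanations are live. The protocol does not accept absence of bleeding as enough after hysterectomy, where it asks for FSH. It does not carry that caution over to other situations in which bleeding is absent for a reason other than menopause.

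Two things are at stake. One is the population: a rule followed to the letter can admit women outside the group named in both aims, in a single-arm study with no control group against which to judge their course. The other is protection. A woman who could become pregnant might receive the infusion and the DXA and QCT scans on the strength of a menstrual history plus whatever the general medical history brings out.

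**Working it through.** The documents give no figure to reproduce, because this is a question of eligibility logic. The check has three steps.

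**Step 1: apply inclusion 2 literally.** FSH stands after the semicolon and the word or, so it belongs to the second branch only. In each case below the woman is aged 30 and meets no exclusion unless one is noted.

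| Woman | Time rule | FSH required? | Outcome |
|---|---|---|---|
| Uterus present, progestin-only method, no spontaneous menses for over 36 months | Met (branch 1) | No | Qualifies |
| Uterus present, anovulatory amenorrhea for over 36 months | Met (branch 1) | No | Qualifies |
| Hysterectomy over 36 months ago | Met (branch 2) | Yes, above 40 | Qualifies only if FSH confirms |
| Uterus present, current estrogen use | May be met | No | Removed by exclusion 18 |

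The word spontaneous does not close the gap. Read literally, drug-induced bleeding does not restart the 36-month clock.

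**Step 2: look for a later check.**

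- The screening draw in section IV tests the remaining eligibility criteria, and branch 1 contains no laboratory criterion.
- The complete medical history in section IV confirms eligibility against the same written rule.
- Exclusion 18 lists estrogens, SERMs and calcitonin, but not progestins.
- Exclusions 9, 10 and 12 (recent malignancy, radiation therapy, major psychiatric disease) may remove some other causes of amenorrhea. They do not address progestin use or anovulation as such.
- None of the 23 exclusions names pregnancy, lactation or childbearing potential. No pregnancy test appears among the study procedures, and section VII does not discuss pregnancy.

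**Step 3: size.** Let k be the number of such women among the 10 enrolled, all analyzed. Their share of the sample is k/10. The documents do not allow k to be estimated. Taking k = 0 to 2 as an assumption, the share is 0/10 = 0% to 2/10 = 20%, with 1/10 = 10% per woman.

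This is a share of participants, not a shift in a result. For a mean change, the shift is (k/10) × D, where D is the difference in mean change between such women and the postmenopausal participants. For each percentage point of D, the sample mean moves by 0.1 point if k = 1 and 0.2 point if k = 2. The documents give no value of D for any outcome. They give a direction only for bone loss after RYGB, from section I. By that statement the bone density change, which section VI classes as exploratory and assesses with within-group t-tests, could look better preserved.

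**The case against.** The strongest reply is that the written rule is not the only safeguard. A physician or nurse practitioner obtains consent, a complete medical history is taken to confirm eligibility, and a questionnaire records medication use. Any of these could reveal progestin use or another cause of amenorrhea, and section IV says plainly that the women enrolled are to be postmenopausal. The study is also a 10-person pilot that section VI says is not powered for bone markers or bone density. It already pools men with women and RYGB with SG, and one atypical participant could be identified and described.

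Much of this stands as a limit on the consequence. It does not repair the criterion: a clinician who discovers progestin use has no written ground for turning the woman away.

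Four stronger readings are tempting, and the documents do not support them.

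- A reader might infer that any woman with long amenorrhea gets in. That is true of inclusion 2 taken alone, but the exclusions still apply, and exclusion 18 removes current and recent estrogen and SERM users.
- A reader might infer bias in the primary outcome, percent change in CTX. Section I speaks only of bone loss after RYGB. Nothing compares CTX or P1NP by menopausal status, nothing on this point covers SG, and the comparison is with younger women in general, not with women who have had long amenorrhea.
- A reader might call the hysterectomy branch faulty too, because the date of surgery does not date menopause. FSH above 40 already confirms current status there, and no aim requires three years since menopause.
- A reader might conclude that the study has no pregnancy safeguard at all. The consent pages and a figure in section IV are not available, so the observation is confined to the visible protocol text.

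**Conclusion.** The concern holds, with limited reach. Branch 1 of inclusion 2 lets women with a uterus qualify as postmenopausal from age 25 on menstrual history alone, and the text available contains no other criterion that would remove a younger woman with progestin-related or anovulatory amenorrhea. That conflicts with the population named in both aims and in section IV. It also leaves the visible protocol with no pregnancy or childbearing-potential criterion ahead of the infusion and scans.

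The logical gap is certain on the text. Its practical size is not: the number affected is unknown and may be zero. A direction of effect is supported only for the exploratory bone density change, and only on the assumption that a woman with non-menopausal amenorrhea resembles the younger women described in section I. No effect on CTX or P1NP is established. The correction is worth making because it is cheap and the rule, not its application, is what admits the wrong women.

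**What to change.** Amend section III in three places:

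1. In inclusion 2, require FSH above 40 units/liter for women in the first branch who are below an age set by the sponsor, measured on the blood already drawn at screening.
2. State that amenorrhea during progestin use does not count as time since last spontaneous menses.
3. Add an exclusion for pregnancy or childbearing potential, and state how it is verified before the infusion and scans.

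The cost is one amendment and one added assay for some women; FSH is already a screening measure for the hysterectomy branch. The downside is that a few truly postmenopausal women with FSH at or below 40 would be excluded. Confining the FSH requirement to younger women limits that loss.
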